7.7 Efficacy Analysis

7.7.1 Analysis of Primary Endpoint

The primary efficacy endpoint is change from baseline in peak esophageal intraepithelial eosinophil count at Week 4.

The change from baseline will be summarized as the n, mean, standard deviation, median, minimum, and maximum by the treatment group of interest using the FAS. Analysis will also be done using the SAS.

7.7.2 Analysis of Secondary Endpoint(s)

For the secondary endpoints, continuous variables will be summarized using the descriptive statistics (n, mean, standard deviation, median, minimum, and maximum) for each observed measurement and change from baseline at each time point by treatment group while categorical variables will be summarized using the counts and percentages as applicable. The FAS will be used for this evaluation. Analysis will also be done using the SAS.

Dysphagia Symptom Questionnaire (DSQ)

The DSQ is used to measure the frequency and intensity of dysphagia. The DSQ scores can range from 0 to 84, with a lower score indicating less frequent or less severe dysphagia.

The questionnaire will be completed by participants daily. Each evening before bedtime, participants will be asked to indicate if they experienced dysphagia symptoms (eg, food passing slowly or food sticking) during that day. Participants must have experienced dysphagia (response of “yes” to Question 2 on DSQ) on a minimum of 2 days total and completed the DSQ on $\geq 70\%$ of days in at least 2 consecutive weeks (qualifying period) prior to the baseline visit (Visit 1). Participants must fill out the DSQ at least 5 or more days during a given week in order to be compliant. Calculations will be performed on daily ePRO entries from the qualifying period prior to baseline, and prior to each study visit during the treatment and follow-up periods. The DSQ score for the secondary endpoints will be calculated by summing the scores of responses to Questions 2 and 3 only. Questions 1 and 4 will be excluded from the DSQ score.

$$\text{DSQ score for 14-day period} = \frac{(\text{Sum of points from questions 2+3 in the daily DSQ with non-missing data over the interval being reported}) \times 14}{\text{Number of diaries reported with non-missing data over the interval being reported}}$$

For each DSQ calculation, the sum of the specified question(s) from each reported daily diary with non-missing data over the interval being reported will be obtained, dividing this by the number of reported daily diaries with non-missing data in that same interval. This result will then be multiplied by the interval. This normalizes each DSQ sum over the interval. For the DSQ score, if a response of “No” is recorded for Question 2, the DSQ score will be set to zero for that day. The DSQ calculations during the interval being reported prior to the baseline visit will be defined as the baseline DSQ evaluation. For each 14-day period, at least 8 reported diaries are needed to effectuate a DSQ calculation for that period. If at least 8 diaries are not available, the DSQ result for that 14-day period will be set to missing.

The absolute change in DSQ score from baseline will be summarized as the n, mean, standard deviation, median, minimum, and maximum by treatment group.

Additionally, exploratory endpoint analysis of absolute days without dysphagia will be summarized as the n, mean, standard deviation, median, minimum, and maximum by treatment group. Absolute days without dysphagia will be obtained through a counting process of the number of DSQ records between baseline and Week 8 that the participant reports DSQ question #2 as “No.”

Esophageal intraepithelial Eosinophil

The proportion of participants achieving peak esophageal intraepithelial eosinophil count of < 15 eos/hpf (Week 4) will be summarized using frequency and percentage.

Also, percent reduction in peak esophageal intraepithelial eosinophil count (eos/hpf) (Week 4) will be summarized as the n, mean, standard deviation, median, minimum, and maximum by treatment group.

Also, exploratory endpoint analysis will be performed for esophageal intraepithelial eosinophil. The proportion of participants achieving peak esophageal intraepithelial eosinophil count of ≤ 1 and ≤ 6 eos/hpf (400 \times) at Week 4 will be summarized separately using frequency and percentage.

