8.3. Participant Withdrawal Criteria

8.3.1. Withdrawal of Participants

Participants are free to withdraw from the study at any time without giving reasons. Furthermore, the investigator may withdraw a participant for reasons such as intolerance to study treatment, intercurrent illness, need for medication that is contraindicated, significant noncompliance with the requirements of the study, or withdrawal of consent. The investigator will assess the reasons for withdrawal as far as possible and will fully record the circumstances and medical details.

Participants who permanently discontinue study treatment and who do not withdraw from the study will be asked to return to the clinic for all remaining study treatment visits and participate in all follow-up assessments according to the visit schedule.

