2.4 Randomization

Approximately 36 participants will be randomized in a 1:1:1 ratio to receive IRL201104 4 mg or 8 mg or placebo according to a central randomization scheme provided by an interactive web response system (IWRS).

Participants who discontinue from the study will be replaced if they did not receive 3 doses of study treatment and the final endoscopy as randomized.

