Handling of Missing Data: Imputation of missing data will not be performed and will be analyzed as missing. To handle missing or partial AEs and concomitant medication dates, the following rules will be applied.

For partial Start Dates:

1. If the year is unknown, then do not impute the date but assign a missing value.
2. If the month is unknown, then:
 - i. If the year matches the year of the first dose date, then impute the month and day of the dose date.
 - ii. Otherwise, assign “January.”
3. If the day is unknown, then:
 - i. If the month and year match the month and year of the first dose date, then impute the day of the dose date.
 - ii. Otherwise, assign “01.”

For partial end dates:

1. If the year is unknown, then do not impute the date but assign a missing value.
2. If the month is unknown, then assign “December.”
3. If the day is unknown, then assign the last day of the month.

After implementing the rules above, to determine whether AEs (or medications) with missing start or stop dates are pre-treatment or on/after treatment, the following strategy will be used:

1. If the start date and stop date are both missing, then the most conservative approach is taken and the AE (or medication) is considered to be treatment emergent (or concomitant medication).

2. If the start date is missing but the stop date is not missing and is on or after the date of signed informed consent, then the most conservative approach is taken, and the AE (or medication) is considered to be treatment emergent (or concomitant medication).
3. If the start date is missing but the stop date is not missing and is before the date of signed informed consent, then the AE (or medication) is considered to be before treatment (or prior medication).
4. If the start date is not missing but the stop date is missing, then the most conservative approach is taken, and medication is considered to be concomitant while the AE is defined by start date.
5. If the Adverse Event Relationship flag is missing, the relationship for adverse event will be imputed and will be considered as Definitely related. If the Adverse Event Severity flag is missing, the severity will be imputed and will be considered as severe & undesirable (Grade 3).

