5.3 Exploratory Endpoints

- Proportion of participants achieving peak esophageal intraepithelial eosinophil count of \leq 6 eos/hpf (400 \times) at Week 4
- Proportion of participants achieving peak esophageal intraepithelial eosinophil count of \leq 1 eos/hpf (400 \times) at Week 4
- Relative change in the EDP transcriptome signature (Week 4)
- Relative change in immune cells and markers of inflammation pre- and postdose administration at screening, baseline, and Weeks 1, 2, 4, 6, and 8. Immune cells and markers of inflammation include: immune cell phenotyping (T-subsets, B-subsets, and macrophage subsets); A20; serum cytokines; serum IgE/IgG4; and serum eosinophil derived neurotoxin (EDN) for eosinophil activation.
- Absolute change in EoE-EREFs (Week 4)

- Absolute change in EoE grade score from the EoE Histology Scoring System (EoEHSS) (Week 4)
- Absolute change in EoE stage score from the EoEHSS (Week 4)
- Proportion of participants with use of rescue medications or procedures (up to Week 8)
- Concentration of functional IRL201104 (up to Week 8)
- Incidence of treatment-emergent antidrug antibody (ADA) responses (Week 8)
- Absolute days without dysphagia.
- Change in PGI-S and PGI-C.

Note that an additional exploratory endpoint: absolute change in severity and/or frequency of EoE symptoms other than dysphagia (up to Week 8) was included in the protocol but will not be evaluated because the relevant information is being captured only as part of the screening visit evaluation. It was inadvertently left in the most current version of the protocol.

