6 ANALYSIS POPULATION AND TREATMENT GROUPS

6.1 Analysis Population

Full Analysis Set: The full analysis set (FAS) will consist of all participants randomized at baseline who receive at least one dose of treatment and who had a baseline and at least one post-baseline measure of the primary or any one of the secondary endpoints. Efficacy evaluations will consider participants according to the treatment group to which they were assigned.

Safety Analysis Set: The safety analysis set will include all participants who were documented to have taken at least 1 dose of study treatment. Safety evaluations will consider participants according to the actual treatment they received.

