7.7.3 Analysis of Exploratory Endpoint(s)

The Exploratory endpoints will be summarized using the FAS.

Patient Global Impression of Severity (PGI-S)

The PGI-S is a PRO measure that uses a verbal rating scale of severity. The PGI-S uses a recall period that aligns with the assessment period used for calculating DSQ endpoint scores (ie, DSQ endpoints are based on 14-day scores, and the PGI-S is administered on the last day of the 14- day assessment period. The PGI-S instructs participants to recall over the past 14 days, such that the anchor covers the same 14-day period as the 14-day DSQ endpoint score).

A numeric scoring for the PGI-S would be 0, 1, 2, and 3. Therefore, while the PGI-S will be summarized categorically, this measure will be also summarized as change from baseline to post-baseline visits.

Patient Global Impression of Change (PGI-C)

The PGI-C is a PRO measure that assesses change compared with prior to starting treatment and reflects the participant's belief about the efficacy of treatment. The PGI-C is a scale depicting a participant's rating of overall improvement.

A numeric scoring for the PGI-C it would be -2, -1, 0, 1, 2. Therefore, the PGI-C will be summarized using categorical and continuous variable summary statistics.

Eosinophilic Esophagitis-Endoscopic Reference Score (EoE-EREFS)

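### Dysphagia-free days are a raw count of diary records, so unfilled diaries and days after leaving the study score the same as days with dysphagia (exploratory endpoint; minor)

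*SAP*

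**What the plan says.** SAP 5.3 lists "Absolute days without dysphagia" among the exploratory endpoints. The protocol lists it too (6.4.3) but gives no derivation. The derivation is in SAP 7.7.2: "Absolute days without dysphagia will be obtained through a counting process of the number of DSQ records between baseline and Week 8" on which Question 2 is answered No. The count is then summarised by arm with the usual descriptive statistics. No denominator, minimum number of diaries or rule for days after withdrawal is given.

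Other relevant provisions:

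- **DSQ score (SAP 7.7.2).** It comes from the same diary, but is formed by "dividing this by the number of reported daily diaries with non-missing data in that same interval" and scaled to 14 days. It is set to missing when fewer than 8 diaries are available.
- **Analysis set.** SAP 7.7.3: "The Exploratory endpoints will be summarized using the FAS". SAP 6.1 admits treated, randomised participants with a baseline and "at least one post-baseline measure of the primary or any one of the secondary endpoints".
- **Replacement (SAP 2.4).** "Participants who discontinue from the study will be replaced" if they did not have all three doses and the final endoscopy.
- **Missing data (SAP 3).** "Imputation of missing data will not be performed and will be analyzed as missing".
- **Stopping treatment (Protocol 8.3.1).** Participants who stop treatment but stay in the study "will be asked to return to the clinic for all remaining study treatment visits".
- **Disposition (SAP 7.1).** Study discontinuation is tabulated by arm and week interval. No table of diary completion by arm is described.

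**The concern.** A count of No records rises with dysphagia-free days, with diaries filled in and with time in the study. A person who skips a diary or leaves loses those days from the count, as if each had been a dysphagia day. The arm mean therefore mixes symptoms with compliance and retention.

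Truncated counts do reach the summary. Replacement adds a participant but does not remove the one who left. A participant leaving at Day 14 with a baseline score and at least 8 post-dose diaries has a post-baseline DSQ score, and so meets the full analysis set definition. The display of missing values in SAP 3 would not flag the problem, because a truncated count still contributes to n.

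The study has no formal test or model, so the tabulated means are what readers will compare. With about 12 participants per arm, a few short records could shrink or reverse a difference, or uneven completion could create one.

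**Working it through.** The plan gives no figure for this endpoint, so there is nothing to reproduce. The following is an illustration.

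**Inputs from the documents**
- Planned completers: 36, randomised 1:1:1, so 36/3 = 12 per arm (SAP 2.3, 2.4).
- Counting period: baseline to Week 8, nominally 56 days (SAP Table 1).
- Compliance floor: 5 diaries in 7 days (SAP 7.7.2).

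**Assumptions, because the documents give no rates**
- A constant dysphagia-free rate p, shown at 40%, 50%, 55% and 60%.
- Participants who leave after 14 days had full diaries until then. They have no Week 4 endoscopy, so they are replaced, and they stay in the full analysis set. The arm is then 12 completers plus k leavers.

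**1. Leavers at Day 14.** Arm mean = (12 × 56p + k × 14p)/(12 + k).

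One leaver (k = 1):
- p = 50%: (12 × 28 + 7)/13 = 26.38 against 28.0, a loss of 1.62 days.
- p = 40%: (12 × 22.4 + 5.6)/13 = 21.11 against 22.4, a loss of 1.29 days.
- p = 60%: (12 × 33.6 + 8.4)/13 = 31.66 against 33.6, a loss of 1.94 days.

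Several leavers, all in the better arm, against a complete 50% arm (28.0 days):
- 60% arm, true advantage 0.10 × 56 = 5.6 days. Three leavers: (12 × 33.6 + 3 × 8.4)/15 = 28.56, so the advantage shrinks to 0.56. Four leavers: (12 × 33.6 + 4 × 8.4)/16 = 27.3, so the order reverses.
- 55% arm, true advantage 0.05 × 56 = 2.8 days. Two leavers: (12 × 30.8 + 2 × 7.7)/14 = 27.5, so the order reverses.

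**2. Leaver at Week 4, after the endoscopy.** This person has had three doses and the endoscopy, so is not replaced. At p = 50% the count loses 0.5 × 28 = 14 days, which costs the arm mean 14/12 = 1.17 days.

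**3. Unfilled diaries, no leavers, no symptom difference (p = 50%).**
- 80% completion: 0.5 × 0.8 × 56 = 22.4 days.
- 90% completion: 0.5 × 0.9 × 56 = 25.2 days, a gap of 2.8 days.
- A participant at the compliance floor completes 56 × 5/7 = 40 diaries and scores 20 instead of 28.

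**4. The same cases as a proportion of completed diaries.** Under the constant-rate assumption the expected values remain 60%, 55% or 50%, whatever the number of diaries. Both reversals and the 2.8-day gap disappear.

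**The case against.** The strongest reply is that the count follows the protocol's own name for the endpoint. The endpoint is exploratory in a study without formal analysis, and the symptom measure that ranks as secondary, the DSQ score, is already normalised. All of that stands, and it limits the importance of the point.

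Mitigations also exist. Compliance is checked at each visit from baseline, participants who stop treatment are asked to keep attending, and discontinuation by week interval will be visible by arm. These narrow the problem mainly to people who leave the study and to skipped diaries. They do not correct the count, and diary completion by arm is not shown.

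Three stronger readings are tempting but not supported:

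- **That early departures are expected.** The replacement rule is a contingency. Neither document gives a dropout rate, and the margin from about 50 enrolled to 36 completing does not separate screening failures from dropouts.
- **That the count breaks the missing-data rule in SAP 3.** That rule forbids imputation, and counting observed No records imputes nothing. The rule simply does not say when a truncated count should become missing. The real contrast is with the DSQ score's denominator and minimum.
- **That three early leavers would reverse a 10-point difference.** This follows only if the arm is held at 12 including the leavers: (9 × 33.6 + 3 × 8.4)/12 = 27.3. It overlooks replacement; with replacements added, three leavers leave 28.56 against 28.0.

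**Conclusion.** The point holds as a minor one. As defined, dysphagia-free days depend on diary completion and time in the study, and nothing else in the SAP removes that dependence. Under the stated assumptions, one early leaver costs the arm mean about 1.3 to 1.9 days, and a 10-percentage-point gap in completion produces 2.8 days with no symptom difference. Reversing a 5.6-day advantage takes four early leavers, all in the better arm; reversing a 2.8-day advantage takes two.

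Whether completion or dropout will differ between arms is unknown, so neither the presence nor the direction of a distortion can be inferred. If both are similar across arms, the counts are lower than the true number of days but the arms are distorted alike. With complete diaries and equal follow-up there is no error. The primary endpoint, the DSQ score and the safety results are unaffected.

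**What to change.** In SAP 7.7.2, make the main summary a per-participant proportion:

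- **Numerator:** completed post-dose diaries up to Week 8 with Question 2 answered No.
- **Denominator:** completed post-dose diaries up to Week 8.
- **Missing** if fewer than 8 such diaries are completed, borrowing the DSQ score's minimum.

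Summarise it by arm with the statistics already planned, and show the number of completed diaries by arm beside it. Keep the raw count as a supportive summary, because the protocol names it.

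The cost is SAP wording and programming; no new data are needed. There are two drawbacks. The proportion assumes that unfilled days resemble filled ones, as the DSQ score already does. An early leaver's proportion also rests on few, early diaries yet carries full weight in the mean: the minimum of 8 is only 8/56 = 14% of the period. The row of completed diaries lets the reader see this.

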7.7.3 Analysis of Exploratory Endpoint(s)

The Exploratory endpoints will be summarized using the FAS.

Patient Global Impression of Severity (PGI-S)

The PGI-S is a PRO measure that uses a verbal rating scale of severity. The PGI-S uses a recall period that aligns with the assessment period used for calculating DSQ endpoint scores (ie, DSQ endpoints are based on 14-day scores, and the PGI-S is administered on the last day of the 14- day assessment period. The PGI-S instructs participants to recall over the past 14 days, such that the anchor covers the same 14-day period as the 14-day DSQ endpoint score).

A numeric scoring for the PGI-S would be 0, 1, 2, and 3. Therefore, while the PGI-S will be summarized categorically, this measure will be also summarized as change from baseline to post-baseline visits.

Patient Global Impression of Change (PGI-C)

The PGI-C is a PRO measure that assesses change compared with prior to starting treatment and reflects the participant's belief about the efficacy of treatment. The PGI-C is a scale depicting a participant's rating of overall improvement.

A numeric scoring for the PGI-C it would be -2, -1, 0, 1, 2. Therefore, the PGI-C will be summarized using categorical and continuous variable summary statistics.

Eosinophilic Esophagitis-Endoscopic Reference Score (EoE-EREFS)

The EoE-EREFS will be used to measure the endoscopically identified EoE esophageal mucosal inflammatory and remodeling features. This instrument includes a total of 17 items related to the presence and severity of esophageal features. The specific esophageal features include: rings (absent, mild, moderate, severe, not applicable); stricture (yes, no, not applicable); diameter of the stricture (if applicable); exudates (absent, mild, severe); furrows (absent, mild, severe); edema (absent, present); crepe paper esophagus (absent, present); overall general appearance incorporating all endoscopically identified EoE findings (ie, fixed rings, strictures, whitish exudates, furrowing, edema, and crepe paper mucosa). In addition, mucosal changes associated with gastroesophageal reflux disease (GERD) will also be recorded using the Los Angeles classification system for erosions (No Erosions or LA Classification A, B, C, D). The EoE esophageal characteristics will be analyzed based on the EoE-EREFS, a validated scoring system for inflammatory and remodeling features of disease using both overall scores and scores for each individual characteristic ([Hirano 2013](#)). The EoE-EREFS should be performed by the physician who performs the endoscopy procedure at the time of the endoscopy. In addition to the local read, images will be submitted to the central imaging laboratory for central reading.

The EoE-EREFS will be summarized descriptively by absolute change from baseline to week 4 by treatment group. Centrally and individual site locally read data will be summarized both across sites and by site. Maximum features (highest score for each feature including both proximal and distal areas) EoE-EREFS will also be summarized across sites.

Eosinophilic Esophagitis-Histology Scoring System

The EoEHSS is a validated histology scoring system for esophageal biopsies that evaluates 8 features: eosinophil density, basal zone hyperplasia, eosinophil abscesses, eosinophil surface layering, dilated intercellular spaces, surface epithelial alteration, dyskeratotic epithelial cells, and lamina propria fibrosis (absent/present) ([Collins 2017](#)). Severity (grade) and extent (stage) of abnormalities will be scored using a 4-point scale (0 normal; 3 maximum change).

Absolute change in EoE grade score and EoE stage score from the EoE Histology Scoring System (EoEHSS) (Week 4) will be summarized separately using descriptive statistics.

For the exploratory EoE-ERES and EoEHSS endpoints, a categorical summary of the scores will be obtained using frequency count and percentage along with the mean, standard deviation, median, minimum, and maximum change from baseline.

Rescue Medications

Use of rescue medication will be summarized separately. The proportion of participants with use of rescue medications or procedures (up to Week 8) will be summarized using frequency and counts. Separate listing will be provided.

ADA (Antidrug antibody)

Antidrug antibody status (negative or positive based on whether results are lower or higher, respectively, than the optical density OD cut-off value) will be listed and summarized by treatment group and time point at scheduled visit based on the Safety Analysis Set.

Incidence of treatment-emergent antidrug antibody (ADA) responses (Week 8). This data will be summarized using frequency, count and percentage.

